### **2.2 Secondary Objective (or Aim)**

Aim 2a: To describe total IgG levels and specific seroprevalence for pneumococcus, varicella, and measles at approximately 3, 6, and 12 months following completion of therapy in patients with ALL

Aim 2b: To describe B and T lymphocyte subset recovery, specifically CD4+ Tfh, using PMBCs at approximately 3, 6 and 12 months following completion of ALL

- Sub-aim: To examine the immune function markers as outlined above in patients who received the monoclonal antibody blinatumomab as part of their ALL treatment regimen versus patients who did not receive blinatumomab.

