## **3 INVESTIGATIONAL PLAN**

### **3.1 General Schema of Study Design**

This is a prospective, multicenter observational study that will assemble a cohort of approximately 115 patients that recently completed or are about to complete ALL therapy at

---

one of several pediatric hematology/oncology centers in the US (CHOP, Lurie Children's Hospital of Chicago, Seattle Children's Hospital, DeVos Children's Hospital, Children's Hospital at Vanderbilt, Christus Children's Hospital (Baylor College of Medicine), and Children's Hospital Los Angeles), including a sub-cohort of 20-25 patients who received blinatumomab as part of their chemotherapy regimen. The same 115 individuals will contribute to both Aim 1 and Aim 2 (Figure 1 and Figure 2). Only patients receiving care at a participating site will be eligible for enrollment in this cohort.

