#### **3.2.2 Total Number of Study Sites/Total Number of Subjects Projected**

The study will be conducted at seven investigative sites in the United States. Other sites may be added in the future. It is expected that approximately 115 subjects will be enrolled over the course of this study to produce 110 evaluable subjects. Evaluable patients will be defined as patients that are enrolled and at least one blood specimen collected.

For each of the 110 enrolled evaluable subjects in the ALL cohort, at the end of the follow-up period, three age- and sex-matched healthy control patients will be selected for comparison, to assemble a cohort of 330 total healthy control patients. The full cohort,

---

including both ALL patients and 3:1 matched controls, is anticipated to include 440 evaluable patients.

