#### **5.1.2.1.2 Blood Specimen Testing Pneumococcal, Varicella zoster virus (VZV), and Measles virus immunoglobulin G (IgG) and Total IgG for ALL cohort participants**

Blood samples collected at each visit will be processed for serum extraction. Serum will be stored locally and batched shipped to the central laboratory for performance of the following antibody specific assays: Pneumococcal 23 serotype specific IgG (1, 2, 3, 4, 5, 6B, 7F, 8, 9N, 9V, 10A, 11A, 12F, 14, 15B, 17F, 18C, 19A, 19F, 20, 22F, 23F, and 33F). These 23 Pneumococcal serotypes were included because, as a group, they account for approximately 90% of invasive pneumococcal infections. Additionally, varicella zoster virus (VZV) and measles virus IgG assays will be performed. Testing for these assays will be performed by Mayo Clinic BioPharma Diagnostics. Participant results will be compared to standard age specific reference ranges of healthy children.

Serum from these samples will also be used to obtain a total IgG level to aid in interpretation of pneumococcal, varicella, and measles IgG results. This testing will be performed at the CHOP Translational Core Laboratory.

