## 6 STATISTICAL CONSIDERATIONS

### 6.1 Primary Endpoint

The primary endpoint for Aim 1 of this study is to determine the incident infection rate in a cohort of subjects in the first year following completion of ALL therapy. Infections will include both clinical and/or microbiologically confirmed infections. All unique infections for a given subject will be captured and included in the final infection rate per person time estimate. Infections will also be reported in subsets of infections such as microbiologically confirmed (i.e., bacteremia, urinary tract infection or pneumonia with a positive sputum culture) or clinically defined infections. Additionally, a specific subset of infections to be described are sinopulmonary infections. This will include a medical encounter for otitis media, sinusitis, or pneumonia for which an antibiotic was prescribed. Infection events for matched healthy control patients will also be captured and used for comparison to the incident infection rate determined for the ALL participants.

The primary endpoint for Aim 2a is the proportion of patients with measles, varicella and pneumococcus antibodies at each study timepoint. Of note, pneumococcal serology results will include 23 serotypes: 1, 2, 3, 4, 5, 6B, 7F, 8, 9N, 9V, 10A, 11A, 12F, 14, 15B, 17F, 18C, 19A, 19F, 20, 22F, 23F, and 33F. Patients with detectable antibody to 50% or more of these serotypes will be considered to have seroprevalence for pneumococcus. This aim will also describe the total IgG levels at each time point at the individual and cohort level. Understanding the total IgG level will inform interpretation of vaccine-specific serology measures.

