### **6.3.3 Analysis of Aim 2**

The total IgG levels and specific seroprevalence proportions for each of the three pathogens (measles, pneumococcus, and varicella) of interest will be determined for the entire cohort and by demographics (e.g. age, race, gender) at each study follow-up time point (i.e. about 3, 6 and 12 months). Additionally, seroprevalence at each time point will be described for subjects that had and had not completed their primary vaccine series before starting ALL chemotherapy, as well as for those who received blinatumomab as part of their chemotherapy regimen and those who did not.

T and B lymphocyte subsets will be measured for a subset of the 110 enrolled subjects. These measurements will be reported for each subject at approximately 3, 6, and 12 months. The trajectory of these measurements will be displayed graphically across the three timepoints of interest to assess relative recovery of lymphocyte quantities after completion of ALL chemotherapy.

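### Aim 2a reports measles, varicella and pneumococcal serology only as yes/no proportions, discarding graded results that would sharpen the blinatumomab contrast and the change over the year

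*Combined protocol and SAP*

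**What the plan says.** Section 6.1 defines the endpoint: "The primary endpoint for Aim 2a is the proportion of patients with measles, varicella and pneumococcus antibodies at each study timepoint". For pneumococcus it adds the rule "Patients with detectable antibody to 50% or more of these serotypes will be considered to have seroprevalence for pneumococcus". Total IgG is treated differently: "This aim will also describe the total IgG levels at each time point at the individual and cohort level".

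Section 6.3.3 carries this into the analysis. It plans total IgG levels and "specific seroprevalence proportions for each of the three pathogens", overall and by demographics at each visit. It also describes seroprevalence by primary vaccine series and by blinatumomab receipt. No section plans a summary of the serotype count or of measles, varicella or serotype-specific IgG values.

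The sub-aim in section 2.2 is "To examine the immune function markers as outlined above in patients who received the monoclonal antibody blinatumomab" against those who did not. Section 3.1 plans the cohort as "including a sub-cohort of 20-25 patients who received blinatumomab as part of their chemotherapy". Section 3.2.2 gives the total: "It is expected that approximately 115 subjects will be enrolled over the course of this study to produce 110 evaluable subjects". On the assays, section 5.1.2.1.2 says "Participant results will be compared to standard age specific reference ranges of healthy children".

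Section 6.4 calls the Aim 2 outcomes descriptive and gives no power calculation for them. Section 1.2 calls the blinatumomab data exploratory.

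**The concern.** Two of the study's questions are about degree. Section 1.2 asks how immune function, including vaccine-antigen response, recovers with time off therapy. Section 2.2 asks whether markers differ by blinatumomab receipt.

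A yes/no score is a blunt tool for either. Under the 50% rule a child who moves from 2 to 11 serotypes between visits is negative both times and shows no change. A child who moves from 11 to 12 changes status. The count that separates these children must exist, because the rule is computed from it, but no planned summary shows it.

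The risk is that a real difference in antibody breadth or level, or a real gain over the year, goes unseen in a wide interval around a difference in proportions. Section 6.4 says these data will inform the need for revaccination and the design of revaccination studies, and such designs need distributions as well as proportions.

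**Working it through.** The plan states no power figure for Aim 2, so there is none to reproduce.

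**Inputs from the documents.** 23 serotypes (section 6.1), 110 evaluable children (3.2.2) and 20-25 recipients (3.1). The splits are therefore 20 v 90 and 25 v 85. The cut is 0.5 × 23 = 11.5, so 12 or more.

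**Assumed.** Two-sided alpha 0.05 (stated for Aim 1 only), all antibody distributions, and complete data at each visit.

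**Step 1: precision of the planned contrast.** With both proportions at 50%, the 95% half-width of the difference is 1.96 × √(0.25/n₁ + 0.25/n₂).
- 20 v 90: 1.96 × √(0.01250 + 0.00278) = 0.24.
- 25 v 85: 1.96 × √(0.01000 + 0.00294) = 0.22.

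Differences of up to about 22-24 points are thus compatible with an observed difference of zero.

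**Step 2: numeric result against a cut, closed form.** Take a normal (log-scale) result with recipients shifted down by d SD. Power on the full scale is Φ(d√(n₁n₂/(n₁+n₂)) − 1.96). For 20 v 90 and d = 0.693, this is Φ(0.693 × 4.045 − 1.96) = Φ(0.84) = 80%.

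Now cut where 50% of non-recipients are positive. Recipients are then Φ(−0.693) = 24.4% positive, a difference of 0.256. The pooled proportion is (20 × 0.244 + 90 × 0.5)/110 = 0.4535.
- Null SE = √(0.4535 × 0.5465 × (1/20 + 1/90)) = 0.1231.
- Alternative SE = √(0.244 × 0.756/20 + 0.25/90) = 0.1096.
- Power = Φ((0.256 − 1.96 × 0.1231)/0.1096) = Φ(0.13) = 55%.

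With the effect set for 80% power on the full scale (d = 0.69 for 20 v 90, 0.64 for 25 v 85), the same calculation gives:

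| Non-recipients positive | Power on the cut |
|---|---|
| 30% | 38-41% |
| 50% | 55-56% |
| 70% | 61-62% |
| 80% | 60-61% |
| 90% | 53-55% |

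The loss is about 18-27 points at 50-90% positive and about 39-42 points at 30%. It also depends on the test. With the unpooled SE throughout, the 50% example for 20 v 90 gives Φ(0.256/0.1096 − 1.96) = Φ(0.38), about 65%, a loss of about 15 points instead of 25.

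**Step 3: the serotype count, simulated.** Each child's probability of antibody to a serotype is drawn from Beta(ms, (1−m)s), with m the mean share and s = (1−ρ)/ρ. The count is binomial out of 23. A rank-sum test on the count is compared with a two-proportion z test at 12 or more.
- Mean share 35% v 50%, ρ = 0.2: about 70% (20 v 90) and 78% (25 v 85) on the count, against about 50% and 57% on the cut.
- Six mean pairs 15-20 points apart, ρ = 0.2-0.4: loss of about 12-35 points.
- Pairs 10 points apart (40% v 50%, 45% v 55%, 50% v 60%), ρ = 0.2-0.4: loss of about 5-13 points. At 22 v 88, power is about 25-40% on the count and 17-30% on the cut, so both are low.
- Pairs 15-20 points apart, ρ = 0.1: loss of about 4-39 points, smallest where both powers are already high.

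**Step 4: change from 3 to 12 months.** This is a separate calculation, and Step 3's range does not carry over to it. With 110 complete pairs, a latent-normal change set for 80% power on a paired t test and within-child correlation 0.3-0.85, McNemar's test on the cut has about 17-54% power, a loss of about 26-62 points. With beta-binomial counts rising from a mean share of 40% to 45%, power is 48-76% on the count against 26-41% on the cut. Evaluable requires only one blood specimen (section 3.2.2), so 110 pairs is a best case.

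The cut loses power in every setting tried. The amount is set by the assumptions.

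**The case against.** The strongest reply is that Aim 2a is a seroprevalence aim with a stated clinical purpose. Section 6.4 says the estimates will show whether children retain vaccine protection, and section 1.2 frames booster decisions around whether protection is adequate. Those are yes/no questions, so proportions are the right headline. This stands, and it is why the proportions should stay. It does not explain the 50% cut or the absence of any graded summary beside it.

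Second, Aim 2 has no test, alpha or power target, so power is not something the plan can strictly lose. This also stands. A reader might infer that the plan gives up a known amount of power. The documents do not support that: the figures above belong to tests supplied for illustration, on assumed distributions. What carries over to a descriptive study is lower precision and sensitivity.

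Third, a reader might infer that all immune data are dichotomised and that recovery rests wholly on yes/no results. That is wrong. Total IgG stays a level, lymphocyte subsets are shown as trajectories with differences by blinatumomab explored, and Figure 2 assigns the timeline of recovery to Aim 2b. Only the pathogen-specific serology is affected.

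Fourth, it is tempting to make graded measures the primary reading. That goes too far: 23 + 2 = 25 analytes at three visits gives 75 contrasts on 20-25 recipients with no multiplicity plan. That the assays return numbers is also only inferred from the planned comparison with reference ranges. Finally, sections 1.1 and 1.2 say missed vaccinations restart at 6 to 12 months, so a gain by 12 months may be vaccine response and not recovery.

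**Conclusion.** The point holds as a gap in the planned description of Aim 2a. Measles, varicella and pneumococcal results are summarised only as proportions, the 50% pneumococcal cut is unexplained, and graded information already collected goes unused where the sample is smallest. No planned estimate is biased or invalid, and the raw results remain available.

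The direction of the loss is robust and its size is not. For the blinatumomab contrast on the serotype count, about 12-35 points (15-20-point differences in mean share) or about 5-13 points (10-point differences) rests on beta-binomial counts, within-child correlation 0.2-0.4, splits of 20 v 90 or 25 v 85, and a two-sided 0.05 test that the plan does not contain. Change over the year needs its own figures and depends on how many children have both samples. The change is worth making because it costs little.

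**What to change.** In sections 6.1 and 6.3.3, keep the seroprevalence proportions as the Aim 2a endpoint and give the reason for the 50% cut. Add, at about 3, 6 and 12 months, overall and by blinatumomab receipt:

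1. The number of pneumococcal serotypes with antibody (0-23), as median, interquartile range and distribution, with the between-group difference and the within-child change, each with a 95% confidence interval.
2. Where the assay returns a number, geometric mean IgG with 95% confidence interval for measles, varicella and the serotypes, treating values below the detection limit as left-censored.

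Label both supportive and descriptive. Report change over time with vaccine doses received during follow-up noted beside it, and state how many children contribute at each visit and to each change.

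The cost is SAP wording, a few more tables and a detection-limit rule. No new samples, visits or patients are needed. If the measles or varicella assay is qualitative only, the change applies to pneumococcus alone.

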## 5 STUDY EVALUATIONS AND MEASUREMENTS

### 5.1 Screening and Monitoring Evaluations and Measurements

#### 5.1.1 Medical Record Review

Variables to be abstracted into the REDCap™ database from the medical charts of ALL cohort patients enrolled at each site will include the following:

- Date of study days
- Weight
- Height
- Demographics (sex, race, ethnicity)
- Underlying conditions (e.g., type of leukemia)
- Co-morbid conditions
- Laboratory values (e.g. Creatinine, AST, ALT, Bilirubin, coagulation profile, WBC, platelets)
- Level of illness (e.g. need for ICU admission, intubation, vasopressors)
- Immune suppression therapies most recently associated with the qualifying condition
- Vital status at last date of follow-up
- Vaccination records
- Social determinants of health-related data (e.g. block group number (zip code plus 4) of residence, insurance type) (Optional – to be collected only for ALL cohort patients/families who consent to having these data collected and for healthy control patients)

Results from the following reports will be collected when available

- Pathology reports
- All radiology reports
- Microbiology results
- Non-culture mycology testing (e.g., Histoplasma urine antigen)
- Interventional radiology reports
- Surgical and procedural reports (e.g. bronchoscopy, eye and sinus exams)

---

Variables to be collected for matched healthy control cohort patients selected from CHOP's PeRC include:

- Date of study days (assigned to mirror the follow-up period of the matched ALL cohort patients)
- Demographics (sex, race, ethnicity, age)
- Underlying conditions
- Co-morbid conditions
- Laboratory values (e.g. Creatinine, AST, ALT, Bilirubin, coagulation profile, WBC, platelets)
- Details of any infection-related healthcare encounters occurring during the assigned study period (e.g. date of infection(s), lab results related to infection, physical examination findings, medications)
- Level of illness (e.g. need for ICU admission, intubation, vasopressors)
- Vaccination records
- Social determinants of health-related data (e.g. block group number (zip code plus 4) of residence, insurance type)

Results from the following reports will be collected when available and related to infections occurring in the study follow-up period:

- Pathology reports
- All radiology reports
- Microbiology results
- Non-culture mycology testing (e.g., Histoplasma urine antigen)
- Interventional radiology reports

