Outcomes for Aim 2 are descriptive and thus power calculations are not provided. The point estimates for seroprevalence will inform if children retain protection against specific pathogens from vaccination administered prior to their diagnosis of and treatment for ALL. Point estimates for seroprevalence will be described for the entire cohort and by subsets of patient characteristics (e.g., chemotherapy inclusive of blinatumomab). The trajectory of recovery of B and T cell subsets will also be described for the sub-cohort of patients enrolled at CHOP. Differences in trajectories by patient specific characteristic (e.g., chemotherapy inclusive of blinatumomab) will also be explored. These granular descriptive immune function data will inform the need for revaccination in this patient population and if necessary, will provide guidance for the optimal design of revaccination studies.

---

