## 7 STUDY ADMINISTRATION

### 7.1 Data Collection and Management

Data elements for this study will be obtained from outpatient and inpatient medical records managed at the local sites where subjects will be enrolled. Data will also be collected regarding specimen collection and the results of specimen processing. Data will be captured in a REDCap™ database. The data will be gathered and entered by trained data abstractors at the participating sites. Categories of data captured from the health records include, but are not limited to: demographics, baseline characteristics, comorbidities, laboratory results, clinical outcomes, medications received, and imaging, microbiology and pathology results as outlined in section 5.1.1.

The REDCap™ Database will be hosted by CHOP. REDCap™ is a software toolset and workflow methodology that supports the electronic collection and management of research and clinical trial data and relies on a thorough study-specific data dictionary defined in an iterative self-documenting. REDCap™'s Data access group function allows for confidential data entry and storage from multiple sites. At the time of enrollment and data entry initiation a unique study identifier will be assigned to each subject. Each enrolling site will maintain its own master list that will capture the local medical record number and the unique study identifier for enrolled subjects. Only study personnel approved at that site will have access to the site master list. The master list will be maintained in case there are any data fidelity issues in REDCap™ that would require re-abstraction of data. Access of members of the research team to any patient identifiers will be limited to the minimum necessary to carry out the proposed research. In addition, research material will be accessible only to members of the investigative team that have completed all required trainings in the Protection of Human Subjects. Individual site abstractors will only have access to their own site's data, not the data of the entire study from all centers. Study personnel at CHOP will have access to the entirety of the REDCap™ database for the purposes of database management, data cleaning, and data analyses.

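### Aim 2a counts donor antibody as the patient's own: immunoglobulin products are not a named data item, and no analysis step deals with passive antibody

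*Combined protocol and SAP*

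**What the plan says.** **Endpoint.** Section 6.1 states: "The primary endpoint for Aim 2a is the proportion of patients with measles, varicella and pneumococcus antibodies at each study timepoint". For pneumococcus it adds: "Patients with detectable antibody to 50% or more of these serotypes will be considered to have seroprevalence for pneumococcus". With 23 serotypes that means 12 or more. Neither rule depends on where the antibody came from.

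**Total IgG.** It has two roles. It is an outcome in its own right under section 2.2 ("To describe total IgG levels and specific seroprevalence for pneumococcus, varicella, and measles at approximately 3, 6, and 12 months"), and it is the stated aid to reading the serology ("Understanding the total IgG level will inform interpretation of vaccine-specific serology measures"). No rule says how it is to be used.

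**Data items.** In the section 5.1.1 list for ALL patients, the nearest treatment item is "Immune suppression therapies most recently associated with the qualifying condition". Vaccination records are listed; immunoglobulin products are not. Section 7.1 has an open list that includes "baseline characteristics, comorbidities, laboratory results, clinical outcomes, medications received", and Figure 1 mentions therapeutic interventions among the items extracted by hand.

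**Eligibility.** Section 3.3.2 excludes primary immunodeficiency (except related to Down syndrome) but sets no condition on receipt of immunoglobulin.

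**Analysis.** Section 6.3.3 reports total IgG and seroprevalence for the whole cohort at each visit. It also splits seroprevalence by completion of the primary vaccine series before chemotherapy, "as well as for those who received blinatumomab as part of their chemotherapy regimen and those who did not". Section 6.3.4, on bias, does not mention passive antibody.

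**Intended reading.** Section 6.4 states: "The point estimates for seroprevalence will inform if children retain protection against specific pathogens from vaccination administered prior to their diagnosis".

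**The concern.** A patient who has recently received pooled donor immunoglobulin can test positive for measles, varicella and possibly pneumococcus without having made that antibody. The endpoint as written counts this patient as seropositive, and section 6.4 then takes the result as evidence that pre-diagnosis vaccination still protects.

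The aid the plan offers fails in exactly this case. Infusion raises total IgG and the specific titers together, so a passive positive looks like a well-supported true one. Total IgG is also distorted as an outcome. The comparison with age-specific reference ranges in section 5.1.2.1.2 cannot separate donor from own antibody either.

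At stake is the use the plan makes of these figures, which is to inform whether revaccination is needed. The split by completed primary series is exposed too, since a child who never completed the series could test positive passively. Unless exposure is recorded with dates, the investigators could not show afterwards whether the problem was negligible.

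**Working it through.** Aim 2 has no power calculation and no assumed seroprevalence, so there is no figure of the plan's to reproduce. The check has two parts: a reading of the text, and an illustration with assumed inputs.

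**Text.** For the endpoint to mean own immunity, one of four places would have to deal with passive antibody.

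- Eligibility (3.3.1, 3.3.2): no restriction.
- Data items (5.1.1, 7.1, Figure 1): generic categories that might capture a product, but none that requires product or date.
- Endpoint definition (6.1): no condition on source.
- Analysis and bias control (6.3.3, 6.3.4): no exclusion, flag or sensitivity analysis.

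**Illustration.** Inputs, all assumed:

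- s, the share truly positive from own antibody: 60%, with a range of 40% to 80%.
- f, the share of patients whose specimen follows recent exposure: 5% to 20%.
- Every exposed specimen reads positive.
- At first, exposure is unrelated to true status.

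Observed = s + f(1 − s).

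| s | f = 0 | f = 5% | f = 10% | f = 20% |
|---|---|---|---|---|
| 40% | 40% | 43% | 46% | 52% |
| 60% | 60% | 62% | 64% | 68% |
| 80% | 80% | 81% | 82% | 84% |

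For example, 0.60 + 0.40 × 0.20 = 0.68. For scale, the 95% half-width at 60% with 110 patients is 1.96 × √(0.24/110) = 0.092, about 9 points. The bias in the 60% row (2 to 8 points) lies within that, but it has a fixed direction and does not shrink with more patients.

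**What each handling rule does.** Take s = 60% and f = 20%, and let e be the share of exposed patients who are truly positive.

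- All specimens: s + f(1 − e).
- Exposed specimens excluded: (s − fe)/(1 − f).
- Exposed positives not counted as own immunity, full denominator: s − fe.

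| e | All specimens | Exposed excluded | Exposed positives not counted |
|---|---|---|---|
| 60% (unrelated) | 68% | 0.48/0.80 = 60% | 48% |
| 40% (weaker immunity) | 72% | 0.52/0.80 = 65% | 52% |

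Exclusion recovers the true 60% only when exposure is unrelated to true status. If exposed patients have weaker immunity, exclusion also reads high. The first and last columns bracket the truth in both rows.

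**The case against.** **The product may already be collected.** Section 7.1 and Figure 1 have categories wide enough to hold it, and the case report form is not in the documents. This stands. The supportable statement is that immunoglobulin is not a named item, not that it is uncollected. The missing analysis step is unaffected.

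**Aim 2 is descriptive and unpowered.** True, but a misclassified specimen biases a descriptive proportion as much as a tested one.

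**There is other evidence on humoral recovery.** B-cell subsets are measured at the same visits. That is partial help, in about 40 patients, including up to 10 who received blinatumomab.

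Three stronger readings are tempting, and the documents support none of them.

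1. *The blinatumomab comparison is biased by unequal infusion.* Section 1.2 says only that blinatumomab may alter immune reconstitution; nothing mentions differing immunoglobulin use. One can assume 40% against 5% exposure and obtain 0.60 + 0.40 × 0.40 = 76% against 0.60 + 0.40 × 0.05 = 62%, a gap of 14 points, but both rates are invented. With 22 and 88 patients (consistent with the stated 20–25 of 110), the 95% half-width for a difference is 1.96 × √(0.24/22 + 0.24/88) = 0.229, about 23 points.
2. *Exposed specimens should be dropped from the main estimate after a fixed washout.* The documents give no basis for a washout length. Dropping specimens can also create a gap. With the same 40% and 5% exposure, exposed patients 40% truly positive and both groups truly 60%, exclusion gives (0.60 − 0.16)/0.60 = 73% against (0.60 − 0.02)/0.95 = 61%.
3. *The distortion peaks at 3 months and then mimics a decline.* This depends on when products are given, on which the documents are silent. Under continuing replacement there need be no early peak.

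**Conclusion.** The point holds in a limited form. As written, the Aim 2a endpoint counts passively acquired measles and varicella antibody as the patient's own. The same may apply to pneumococcus, depending on how many of the 23 serotypes a product would make detectable. Total IgG is inflated by the same exposure and so cannot serve as the check. The error always runs towards retained immunity, which is the conclusion section 6.4 means to draw.

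The size cannot be fixed from the documents. With 60% truly positive, unrelated exposure and every exposed specimen positive, use in 5% to 20% of patients overstates seroprevalence by 2 to 8 points. It would be more if exposed patients have weaker immunity, less if some exposed specimens read negative, and nothing if no one is exposed. The conclusion also rests on a premise that the documents do not state: pooled donor immunoglobulin carries measles and varicella IgG. A difference between blinatumomab groups remains a possibility to be checked, not a finding.

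**What to change.** **Section 5.1.1:** add immunoglobulin product and date to the list for ALL patients, covering a pre-specified window before each study draw. The investigators should choose and justify that window in advance.

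**Section 6.3.3:**

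- Report the number and share of patients exposed, by time point and by blinatumomab group.
- Keep the all-specimen estimate as the main one.
- Add a pre-specified sensitivity analysis that excludes exposed specimens, for seroprevalence of all three pathogens and for total IgG.
- Add a second one, for seroprevalence only, that treats exposed positives as no evidence of own immunity while keeping the full denominator. This gives a lower bound to set beside the main estimate.

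**Section 6.4:** make the reading as retained vaccine protection conditional on these analyses.

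**Cost:** one field in a chart review already being done, unless the form already holds it, plus SAP wording. Because section 1.2 says most of the cohort is already enrolled, some charts would need a second look; section 7.1 keeps the site master lists so that data can be re-abstracted. The exclusion analysis has a smaller denominator and may remove the patients with the weakest immunity, so it should not replace the main estimate. The change concerns data and analysis only and alters no patient's care.
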